## 4. Study Design

### 4.1. Overall Study Design

This is a Phase 3b, open-label study to evaluate the safety, reactogenicity, and immunogenicity of mRNA-1273 SARS-CoV-2 vaccine in SOT recipients and healthy controls. Adult kidney and liver transplant recipients and healthy control participants who are at least 18 years of age will be enrolled at ~20 sites in US and non-US sites.

Approximately 240 adult participants (220 previously vaccinated or unvaccinated participants who have had a kidney or liver transplant and 20 unvaccinated healthy adults) will be enrolled. At least 50 SOT recipients who completed primary series vaccines with mRNA or non-mRNA COVID-19 vaccine under EUA outside the study will be enrolled in Part B (Group B4).

[figure not shown]
In Part A, all SOT recipients who were unvaccinated prior to enrollment will receive 2 doses of 100  $\mu$ g of mRNA-1273 (vaccine) 28 days apart (window of -3/+7 days for the second dose) (Group A1). The SOT recipients will be offered the opportunity to receive a third dose of vaccine at Day 85 (window of -3/+7 days for the third dose) (Group A2). All healthy participants will receive 2 doses of vaccine 28 days apart (window of -3/+7 days for the second dose) (Group A5). SOT recipients who were previously vaccinated with 2 doses of Moderna COVID-19 vaccine under the EUA prior to enrollment will receive dose 3 on Day 1 (Group A3). These participants will be referred to as previously vaccinated throughout this document.

Under Amendment 4, unvaccinated SOT participants who will be enrolled will be given 3 100  $\mu$ g doses in Part A then proceed to Part B to receive a 100  $\mu$ g booster dose (Group A2 to Group B2). SOT participants previously vaccinated with 2 doses of Moderna COVID-19 vaccine outside of the study who will be enrolled will receive a third 100  $\mu$ g dose in Part A then proceed to Part B to receive a 100  $\mu$ g BD (Group A3 to Group B3). SOT participants who completed primary series vaccines with mRNA or non-mRNA COVID-19 vaccine outside of the study who consent to receive 1 booster dose in Part B (Group B4). Healthy participants who will be enrolled will be given 2 100  $\mu$ g doses in Part A then proceed to Part B to receive a 100  $\mu$ g booster dose (Group A5 to Group B5).

In Part B, all eligible active participants in Part A will be offered to receive a 100  $\mu$ g BD of mRNA-1273 who are at least 4 months from the last dose.

[figure not shown]

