### **5.3. Analysis Populations for Part B**

All participants who are enrolled in Part A and continues to Part B will be considered into analysis populations for Part B. SOT recipients who completed primary series vaccination with an mRNA or non-mRNA COVID-19 vaccine outside of the study who consent to receive BD in Part B will be included in Part B analysis populations.

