#### **5.3.3. Per-Protocol Immunogenicity Set (Part B)**

PP Immunogenicity Set (Part B) includes all participants in the mITT Set (Part B) who received planned BD per schedule, and SOT recipients who completed primary series vaccination with an mRNA or non-mRNA COVID-19 vaccine outside of the study that are in the mITT Set (Part B). The participants who complied with the timings of immunogenicity blood sampling to have post-booster results available for at least one assay component corresponding to the immunogenicity analysis objective, and participant had no major protocol deviations that impact immune response during the period corresponding to the immunogenicity analysis objective will be included.

The PP Immunogenicity Set (Part B) will serve as the primary analysis population for the analysis of SARS CoV 2-specific bAb and nAb immunogenicity data in Part B.

Confidential

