##### **6.4.3.1. Seroresponse Rate (SRR) of the Primary Series and Booster**

For a subset of the antibodies of interest, seroresponse rate, defined as number of subjects achieving seroresponse, will be summarized at each post-baseline timepoint. There will be 2 baseline definitions used for determining seroresponse rate: 1) Pre-vaccination baseline is defined as the sample collected prior to any injection in Part A (primary series) and 2) Pre-booster baseline is defined as the sample collected prior to BD in Part B. Subjects that are enrolled in both Part A and Part B will be analyzed based on both types of baseline (pre-vaccination and pre-booster).

If missing pre-vaccination baseline (no available serum samples), and the subject did not have SARS-CoV-2 infection prior to vaccination (i.e. negative SARS-CoV-2 status at pre-vaccination of primary series), the subject's pre-vaccination baseline antibodies will be Confidential

assumed to be < LLOQ. Similarly, for SOT recipients who completed primary series vaccination with an mRNA or non-mRNA COVID-19 vaccine outside of the study, if pre-booster baseline antibodies are missing and the subject did not have SARS-CoV-2 infection prior to receiving BD (i.e. negative SARS-CoV-2 status), the subject's pre-booster baseline antibodies will be assumed to be < LLOQ.

- Two definitions for seroresponse will be used for analyses: 1) 4-fold rise seroresponse based on pre-vaccination baseline and 2) 4-fold rise seroresponse based on pre-booster baseline. Seroresponse based on pre-vaccination baseline is defined in 2 ways:
  - 4-fold rise seroresponse (primary approach), measured by an increase of SARS-CoV-2 specific bAb or nAb from pre-vaccination baseline < LLOQ to at least  $4 \times$  LLOQ, or a 4-fold or greater rise if pre-vaccination baseline  $\geq$  LLOQ.
  - If assay-specific critical fold rise becomes available, seroresponse based on assay-specific critical threshold may be provided.
- The 4-fold rise definition will be used for seroresponse analyses at each post-baseline for all subjects in Part A (regardless of whether subjects continue to Part B) and all subjects in Part B.
- Seroresponse based on pre-booster baseline follows the same definition as pre-vaccination seroresponse.
- Difference in seroresponse rates between the BD and the primary series and among participant groups may be provided with 2-sided 95% CIs using the Miettinen-Nurminen's method.

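### The booster versus primary-series seroresponse difference is given an independent-samples interval, although the two rates come partly from the same people

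*SAP*

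**What the plan says.** SAP 6.4.3.1 makes the contrast optional and names one method, Miettinen-Nurminen, both for booster against primary series and among participant groups. Up to the name of that method, the sentence reads: "Difference in seroresponse rates between the BD and the primary series and among participant groups may be provided with 2-sided 95% CIs using". No paired method is mentioned.

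The same section shows that the primary series means Part A of this study, not an external control: "Pre-vaccination baseline is defined as the sample collected prior to any injection in Part A (primary series"). It adds: "Subjects that are enrolled in both Part A and Part B will be analyzed based on both types of baseline". Seroresponse by the 4-fold definition is to be analysed "for all subjects in Part A (regardless of whether subjects continue to Part B) and all subjects in Part B".

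SAP 5.3 carries the continuers forward: "All participants who are enrolled in Part A and continues to Part B will be considered into analysis populations for Part B". The Part B immunogenicity set defined in SAP 5.3.3 also admits these people: "SOT recipients who completed primary series vaccination with an mRNA or non-mRNA COVID-19 vaccine outside of the study that are in the mITT Set". They form Group B4, which counts in the booster phase only, and SAP 4.1 gives its size: "At least 50 SOT recipients who completed primary series vaccines with mRNA or non-mRNA COVID-19 vaccine under EUA outside the study will be enrolled". Protocol Table 2 shows A2 moving to B2, A3 to B3 and A5 to B5. It lists Part B as not applicable for A1.

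**The concern.** The Miettinen-Nurminen variance is the sum of two binomial variances. It has no term for the covariance that arises when one person supplies both a primary-series and a booster result. Every continuer does so.

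At stake is the calibration of a reported interval. The study tests no hypotheses and is presented as an estimation study (Protocol section 8; SAP 4.2), so confidence intervals are its main inferential output. If this one is reported, its nominal 95% should mean what it says. SAP 6.4.3.1 also leaves open which subjects enter the contrast and which baseline each rate uses, so the size and the sign of the error cannot be read off the plan.

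**Working it through.** **Plan's own figure.** None is given for a seroresponse difference. The one probability in SAP 4.2 concerns organ rejection: 1 - 0.97^200 = 0.998, which agrees with the stated >95% but does not bear on this point.

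**Who counts where** (SAP 4.1, 5.3, 5.3.3, 6.4.3.1; Protocol Table 2).

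| Group | Primary-series rate | Booster rate |
|---|---|---|
| A2/B2, A3/B3, A5/B5 continuers | yes | yes |
| A1 and other non-continuers | yes | no |
| B4 (at least 50) | no | yes |

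If the 50 are counted within the 220 planned transplant recipients, B4 is at least 50/220 = 22.7% of them. SAP 5.3.1 also removes anyone not negative for SARS-CoV-2 before the booster, which reduces the overlap further.

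**Variance.** With n people per rate, m of them in both, rates pB and pP, and within-person correlation phi:

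Var(pB - pP) = pB(1-pB)/n + pP(1-pP)/n - 2(m/n²)·phi·√[pB(1-pB)pP(1-pP)]

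Miettinen-Nurminen leaves out the last term. Take as assumptions n = 100, pB = 0.80 and pP = 0.60. The first two terms give 0.0016 + 0.0024 = 0.0040, so the SE is 0.0632. With m = 100 the last term is 2 × 0.1960/100 × phi = 0.00392·phi. With m = 70 it is 0.00274·phi.

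| phi | SE, full overlap | 0.0632/SE | SE, 70% overlap | 0.0632/SE |
|---|---|---|---|---|
| -0.3 | √0.00518 = 0.0719 | 0.88 | √0.00482 = 0.0694 | 0.91 |
| 0 | 0.0632 | 1.00 | 0.0632 | 1.00 |
| 0.3 | √0.00282 = 0.0531 | 1.19 | √0.00318 = 0.0564 | 1.12 |
| 0.5 | √0.00204 = 0.0452 | 1.40 | √0.00263 = 0.0513 | 1.23 |

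**Score intervals, same assumed rates, 100 full pairs.** Both methods invert a score statistic at ±1.96. Miettinen-Nurminen uses (pB - pP - d)/√{[r1(1-r1)/n1 + r2(1-r2)/n2]·N/(N-1)}, where N = n1 + n2 and r1, r2 are the estimates restricted to r1 - r2 = d. Tango's paired interval uses (b - c - nd)/√{n[2q + d(1-d)]}, where b people gain a response, c lose one, and q is the restricted estimate of the probability of losing. Miettinen-Nurminen gives 7.4 to 32.2 points (width 24.8) whatever the pairing.

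| phi (approx.) | Tango limits, points | Width | MN/Tango width |
|---|---|---|---|
| -0.3 | 5.5 to 33.6 | 28.2 | 0.88 |
| 0 | 7.3 to 32.2 | 24.9 | 0.99 |
| 0.3 | 9.5 to 30.6 | 21.1 | 1.17 |
| 0.5 | 11.6 to 29.5 | 17.9 | 1.39 |

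The calculation was repeated for 50, 100 and 150 pairs and for three assumed pairs of rates (80/60, 85/75 and 60/60%). The width ratio was 0.87 to 0.90 at phi about -0.3, 0.99 to 1.00 at 0, 1.12 to 1.19 at about 0.3, and 1.31 to 1.40 at about 0.5.

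**Coverage of the nominal 95% Miettinen-Nurminen interval**, simulated with 20,000 replicates, 100 people per rate, true rates 80% and 60%.

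| phi | Full overlap | 70% overlap |
|---|---|---|
| -0.3 | 91.3% | 92.8% |
| 0 | 95.1% | 95.0% |
| 0.3 | 98.1% | 97.2% |
| 0.5 | 99.4% | 98.5% |

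**Sign of phi.** If both responses are judged against the pre-vaccination baseline, the same baseline sample enters both indicators, and a positive phi is expected. If the booster response is judged against the pre-booster baseline, a strong primary responder may start high and find a 4-fold rise harder to reach, so a negative phi is plausible.

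**The case against.** The best defence has three parts.

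*The samples are not fully paired.* This is right. A reader might infer that both rates come from the same people throughout. The SAP does not say so: it takes all Part A and all Part B subjects, and A1 and B4 each count on one side only. For the Pfizer-primed and Other booster groups there is no in-study primary series. A contrast of those groups with Part A is between different people, and Miettinen-Nurminen is then correct. Partial overlap shrinks the error but does not remove it, as the 70% columns show.

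*Nothing rests on the interval.* Also right. The difference is optional. Seroresponse is not among the endpoints in SAP section 3, and the primary immunogenicity analysis is the geometric mean concentration (SAP 6.4.2). No test, margin or sample size depends on it. This lowers the consequence but does not make the named method suitable.

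*The same sentence also covers differences among participant groups, where the method is suitable.* It is, for disjoint groups such as kidney and liver. Because SAP 6.1 also lists nested groups (Total SOTs Who Received 3 Doses contains two others), a reader might infer that a group will be compared with its own subset. No section specifies such a contrast, so this supports only a clarifying restriction.

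**Conclusion.** Wrong as written, with low consequence. For the booster versus primary-series contrast the independent-samples interval is mis-calibrated whenever the within-person correlation is not zero. In the settings examined its width runs from about 0.87 to about 1.4 times that of a paired interval, and closer to 1 under partial overlap. Rates, number of pairs and correlation are all assumptions, because the documents give none.

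A reader might also infer that the interval is always too wide and so would hide a real booster gain. The documents do not support that: the sign of the correlation depends on which baseline is used, and SAP 6.4.3.1 provides for both. Nor do examples chosen at high positive correlation show a changed conclusion. With 50 pairs, 40 against 30 responders, 11 gaining and 1 losing (phi 0.51), the limits are 0.020 to 0.370 by Miettinen-Nurminen and 0.078 to 0.338 by Tango; both exclude zero. With 36 against 30 responders, 8 gaining and 2 losing (phi 0.58), they are -0.067 to 0.299 and -0.005 to 0.255; both include zero.

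**What to change.** In SAP 6.4.3.1:

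1. State which subjects enter the booster versus primary-series contrast, and which baseline each rate uses.
2. For participants with both results, use a paired interval (Tango score or Newcombe paired).
3. If all Part A and Part B subjects are kept, use a method that allows partial overlap, for example GEE with robust variance clustered on participant. This version also reflects differences in who makes up each rate, so it should be labelled accordingly.
4. Keep Miettinen-Nurminen for disjoint groups only.

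The cost is a few lines in the SAP and a change of procedure in the program. No new data are needed.

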#### **6.4.4. Exploratory Analysis of Antibody Responses Meeting Protection Threshold**

If an accepted serum Ab threshold of protection against COVID-19 is available based on data from the P301 study, an additional exploratory analysis will be performed by measuring the proportion of participants with a serum Ab level greater than or equal to the threshold at Day 57 for unvaccinated participants in the 2-dose regimen, at Day 113 for unvaccinated participants in the 3-dose regimen, and at Day 29 for previously vaccinated SOT participants in Part A. Exploratory analysis will be performed at BD-Day 29 and BD-Day 181 for participants who received BD in Part B. A 2-sided 95% CI using the Clopper-Pearson method by participant group will also be calculated. If an accepted serum Ab

Confidential

threshold of protection against COVID-19 is not available, this summary will not be performed.

## **6.5. COVID-19 and SARS-CoV-2 Infection Analysis**

For both Part A and Part B, the mITT Set (Part A/Part B) will be used for the analysis of COVID-19 and SARS-CoV-2 infection starting from 14 days after the second dose and third dose received for each participant group. The PP Set (Part A/Part B) may be used in the analyses as appropriate, unless otherwise specified.

**Baseline SARS-CoV-2 status and Pre-booster SARS-CoV-2 Status** is described in [Section 6.1](#). The serology test results based on Roche Elecsys assay at baseline, and the RT-PCR test results at baseline will be summarized by participant group.

Participants with pre-vaccination baseline positive or missing SARS-CoV-2 status will be excluded from the mITT Set (Part A) infection analysis.

Participants with pre-booster positive or missing SARS-CoV-2 status will be excluded from the mITT Set (Part B) infection analysis.

The post-baseline serology test results based on the Roche Elecsys assay and the RT-PCR test results will also be summarized by visit.

### **6.5.1. Endpoint Definitions/Derivations**

#### **6.5.1.1. SARS-CoV-2 Infection**

This is a combination of COVID-19 (defined in [Section 6.5.1.3](#)) and asymptomatic SARS-CoV-2 infection (defined in [Section 6.5.1.2](#)) for participants with negative SARS-CoV-2 status at baseline. The incidence of SARS-CoV-2 infection counted starting 14 days after the second dose, the third dose, and the BD of IP will be summarized by participant group. SARS-CoV-2 infection will be defined in participants with negative SARS-CoV-2 at baseline meeting the criteria below:

- bAb levels against SARS-CoV-2 nucleocapsid protein negative (as measured by Roche Elecsys) at Day 1 that becomes positive (as measured by Roche Elecsys) counted starting 28 days after the second dose (at Day 57); 28 days after the third dose (at Day 113); and 28 days after the BD (BD-Day 28) or later, OR
- Positive RT-PCR counted starting 14 days after the second dose, third dose, and BD of IP

Confidential

During the analysis, documented infection is counted starting 14 days after the second, third dose, and BD of IP, which requires positive serology test result based on bAb specific to SARS-CoV-2 nucleocapsid 28 days after the second, third dose, and BD, or a positive RT-PCR result starting 14 days after the second, third dose, and BD of IP. Derivation of this endpoint is summarized in [Table 1](#) below.

**Table 1. Derivation for SARS-CoV-2 Infection**

Baseline SARS-CoV-2 Status	Post-baseline assessments		Endpoint: SARS-CoV-2 infection
	RT-PCR test post-baseline	bAb levels against SARS-CoV-2 Nucleocapsid	
Negative at Baseline of each part	Positive (either at scheduled NP swab test, or at symptom-prompt NP swab test 14 days after the second/third dose)		Case
Negative at Baseline of each part		Positive (28 days after the second, third dose, and BD or later) as measured by Roche Elecsys	Case

The date of documented infection will be the earlier of:

- Date of positive post-baseline RT-PCR result, or
- Date of positive post-baseline serology test result based on bAb specific to SARS-CoV-2 nucleocapsid

For Part A, the time to the first documented SARS-CoV-2 infection will be calculated as:

Time to the first SARS-CoV-2 infection = Date of the first infection – Date of first study dose + 1.

For Part B, the time to the first documented SARS-CoV-2 infection will be calculated as:

Time to the first SARS-CoV-2 infection = Date of the first infection – Date of BD + 1.

Cases will be counted starting 14 days after the second, third dose, and BD, e.g., date of documented infection - Date of the second/third dose/BD  $\geq$  14.

Confidential

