7.1.6. Assessments for SARS-CoV-2 Infection

Study participants will have NP samples collected for SARS-CoV-2 testing by RT-PCR at time points specified in the applicable SoE ([Section 10.1](#)). A study illness visit or a consultation will be arranged within 72 hours or as soon as possible to collect an NP or nasal swab sample (NP is preferred) to ascertain the presence of SARS-CoV-2 via RT-PCR if a participant experiences any of the following:

- Signs or symptoms of SARS-CoV-2 infection as defined by the CDC ([CDC 2020a](#))
- Close contact exposure to an individual confirmed to be infected with SARS-CoV-2
- MAAE suggesting a SARS-CoV-2 infection

If the participant had known close contact exposure to COVID-19 (eg, close contact exposure to someone with confirmed COVID-19), it will be captured in the COVID-19 exposure form.

If scheduled, the study illness visit may collect additional clinical information at the investigator's discretion, including but not limited to medical history, physical examination, blood sampling for

clinical laboratory testing, and nasal, saliva, and/or NP swab sampling for viral PCR (including multiplex PCR for respiratory viruses, including SARS-CoV-2) to evaluate the severity of the clinical case. Radiologic imaging studies may be conducted. During this visit, a blood sample will also be collected for immunologic assessment of SARS-CoV-2. All findings will be recorded in the eCRF.

If participants are confirmed to have SARS-CoV-2 infection, the investigator will notify the participant and the participant's primary care physician of the diagnosis. If the study participant does not have a primary care physician, the investigator will assist them in obtaining one. The participant will also be instructed on infection prevention measures consistent with local public health guidance.

Any confirmed symptomatic SARS-CoV-2 infection occurring in participants will be captured as an MAAE along with relevant concomitant medications and details about severity, seriousness, and outcome. Additionally, a convalescent visit will be scheduled approximately 28 days (+7 days) after diagnosis ([Section 7.3.2](#)). At this visit, an NP swab sampling for viral PCR and a blood sample will be collected for potential immunologic assessment of SARS-CoV-2 infection

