15. An unscheduled visit may be prompted by reactogenicity issues, illness visit criteria for COVID-19, or new or ongoing AEs. If a participant meets the prespecified criteria of suspicion for COVID-19 ([Section 7.1.6](#)), the participants will be asked to return within 72 hours or as soon as possible to the study site for an unscheduled illness visit, to include an NP swab sample (for RT-PCR testing) and other clinical evaluations including blood sample collection for immunologic assessment of SARS-CoV-2 infection (bAb against the nonvaccine antigen [nucleocapsid protein]). If a study site visit is not possible, the participant will be asked to submit a saliva sample to the study site by a Sponsor-approved method. At this illness visit, the NP swab samples will be collected to evaluate for the presence of SARS-CoV-2 infection. NP swab samples will also be tested for the presence of other respiratory pathogens. In addition, the study site may collect an additional NP sample for SARS-CoV-2 testing to be able to render appropriate medical care for the study participant as determined by local standards of care. Additionally, clinical information will be carefully collected to evaluate the severity of the clinical case.
16. A convalescent visit will be scheduled approximately 28 days (+7 days) after diagnosis. At this visit, an NP swab sampling for viral PCR and a blood sample will be collected for potential immunologic assessment of SARS-CoV-2 infection.
17. Diary entries will be recorded by the participant at approximately 30 minutes after injection while at the study site with instruction provided by study staff. Study participants will continue to record entries in the eDiary each day after they leave the study site, preferably in the evening, on the day of injection and for 6 days following injection. If a solicited local or systemic AR continues beyond Day 7 after vaccination, the participant will be prompted to capture details of the solicited local or systemic AR in the eDiary until the AR is resolved or the next vaccine injection occurs, whichever occurs first; capture of details of ARs in the eDiary should not exceed 28 days after each vaccination. Adverse reactions recorded in the eDiary beyond Day 7 should be reviewed either via telephone call or at the following study visit.

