### 3.2.2. Secondary COVID-19 and SARS-CoV-2 Infection Endpoints

The incidence of asymptomatic SARS-CoV-2 infection after mRNA-1273 vaccination in adult SOT recipients and healthy adult participants with negative SARS-CoV-2 at baseline will be evaluated by the following endpoints:

The incidence of asymptomatic SARS-CoV-2 infection among recipients of mRNA-1273 SARS-CoV-2 vaccine will be defined in participants with negative SARS-CoV-2 at baseline as:

- bAb levels against SARS-CoV-2 nucleocapsid protein negative (as measured by Roche Elecsys) at Day 1 that become positive (as measured by Roche Elecsys) counted starting 28 days after the second dose and 28 days after the third dose of vaccine, OR
- Positive reverse transcriptase polymerase chain reaction (RT-PCR) (central lab or local diagnostic tests) counted starting 14 days after the second and after the third dose of vaccine

The incidence of COVID-19 after vaccination with mRNA-1273 in SOT recipients and healthy participants will be evaluated by the following endpoints:

- First occurrence of COVID-19 starting 14 days after the second dose and after the third dose of vaccine, where COVID-19 is defined as symptomatic disease based on the following criteria:
  - The participant must have experienced at least TWO of the following symptoms: fever ( $\geq 38^{\circ}\text{C}/\geq 100.4^{\circ}\text{F}$ ), chills, myalgia, headache, sore throat, or new olfactory and taste disorder(s), OR
  - The participant must have experienced at least ONE of the following respiratory signs/symptoms: cough, shortness of breath or difficulty breathing, OR clinical or radiographical evidence of pneumonia, AND
  - The participant must have at least 1 nasopharyngeal (NP) swab, nasal swab, or saliva sample (or respiratory sample, if hospitalized) positive for SARS-CoV-2 by RT-PCR
- First occurrence of severe COVID-19 starting 14 days after the second dose and after the third dose of vaccine, where severe COVID-19 is defined as symptomatic COVID-19 AND any of the following:
  - Clinical signs indicative of severe systemic illness, respiratory rate  $\geq 30$  per minute, heart rate  $\geq 125$  beats per minute, oxygen saturation ( $\text{SpO}_2$ )  $\leq 93\%$  on room air at sea level, or partial pressure of oxygen ( $\text{PaO}_2$ )/fraction of inspired oxygen ( $\text{FIO}_2$ )  $< 300$  mm Hg, OR

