### 6.5.1.2. Asymptomatic SARS-CoV-2 Infection

This is a secondary endpoint for Part A and exploratory endpoint for Part B. It is defined in participants with negative SARS-CoV-2 at baseline. Asymptomatic SARS-CoV-2 infection is identified by both the absence of symptoms and the presence of infection as detected by RT-PCR or serology tests. Specifically:

- Absent of COVID-19 symptoms within 14 days of positive virologic or serologic results
- AND at least one from below:
  - Positive serology test result based on bAb specific to SARS-CoV-2 nucleocapsid at scheduled visits, when blood samples for immunogenicity are collected, or
  - Positive RT-PCR test post-baseline (at scheduled or unscheduled/illness visits)

The date of documented asymptomatic SARS-CoV-2 infection is the earlier date of:

- Date of positive serology test result based on bAb specific to SARS-CoV-2 nucleocapsid, or
- Date of positive RT-PCR test post-baseline (at scheduled or unscheduled/illness visits), with absence of symptoms.

For Part A, the time to the documented asymptomatic SARS-CoV-2 infection will be calculated as:

Time to the asymptomatic SARS-CoV-2 infection = Date of asymptomatic SARS-CoV-2 infection – Date of first study dose + 1.

For Part B, the time to the documented asymptomatic SARS-CoV-2 infection will be calculated as:

Time to the asymptomatic SARS-CoV-2 infection = Date of asymptomatic SARS-CoV-2 infection – Date of BD + 1. Cases will be counted starting 14 days after the second dose and after the third dose, e.g., date of documented infection - Date of the second/third dose/BD  $\geq$  14.

Confidential

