### 6.5.1.3.COVID-19

The incidence of the first occurrence of COVID-19 starting 14 days after the second, third dose, and BD of IP will be presented. COVID-19 is defined as symptomatic disease based on the criteria specified in [Section 3.2.2](#). Cases are defined as participants meeting clinical criteria based on both symptoms for COVID-19 and positive RT-PCR test results.

Surveillance for COVID-19 symptoms will be conducted every two weeks by either telephone calls or eDiary prompts (alternating). Subjects reporting COVID-19 symptoms, as defined in Section 7.3.2 of Protocol Amendment 4, will be arranged an illness visit to collect an NP swab.

For this endpoint, a COVID-19 case will be identified as a positive post-baseline RT-PCR test result, together with eligible symptoms as described below in [Table 2](#).

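### The RT-PCR cell of SAP Table 1 contradicts the definition of SARS-CoV-2 infection in Section 6.5.1.1, so programming from the table could miss cases

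*SAP*

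**What the plan says.** **Table 1 (SAP 6.5.1.1).** The RT-PCR cell accepts a positive "either at scheduled NP swab test, or at symptom-prompt NP swab test 14 days after the second/third dose". A separate row makes a case of anyone whose nucleocapsid antibody is positive 28 days or more after the second dose, third dose or booster.

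**Text of SAP 6.5.1.1.** The section opens: "This is a combination of COVID-19", joined with asymptomatic infection, each by reference to its own section. Its RT-PCR criterion is "Positive RT-PCR counted starting 14 days after the second dose, third dose, and BD of IP", with no limit on specimen or trigger. The text presents Table 1 as a summary of the derivation. Below the table, the infection date uses any positive post-baseline RT-PCR, and a counting line requires at least 14 days from the second dose, third dose or booster.

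**Component endpoints.** Under SAP 6.5.1.3, "a COVID-19 case will be identified as a positive post-baseline RT-PCR test result" with eligible symptoms. The criteria in SAP 3.2.2 allow NP, nasal and saliva samples, and any respiratory sample in hospital. SAP 6.5.1.2 accepts, for asymptomatic infection, "Positive RT-PCR test post-baseline (at scheduled or unscheduled/illness visits".

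**Sampling.** Protocol 7.1.6 arranges an NP or nasal swab after several triggers, one of them being "Close contact exposure to an individual confirmed to be infected with SARS-CoV-2". Under the Schedule of Events footnotes, "If a study site visit is not possible, the participant will be asked to submit a saliva sample to the study site".

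**Reporting.** SAP 6.5.2 tabulates infection, asymptomatic infection and COVID-19 side by side. It also foresees analysing the infection endpoint by NP, nasal and saliva specimen.

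**The concern.** A composite endpoint should contain everyone who meets one of its components. Taken alone, the Table 1 cell breaks that rule: a participant could be a COVID-19 case on a saliva sample, or an asymptomatic infection on an exposure-prompted swab, and not be a SARS-CoV-2 infection. The cell also leaves out the booster, which the text and the table's own serology row include.

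A derivation table is a natural source for a programming specification. If it is used that way, infections are lost from the overall rate, and the three tables produced under 6.5.2 do not add up.

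**Working it through.** No arithmetic in the plan supports or refutes this point, and the plan states no figure to reproduce. The check sets the definitions side by side and then counts scheduled swabs.

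**Step 1: definitions.** Take a participant negative at baseline, RT-PCR positive at least 14 days after the relevant dose, with no nucleocapsid seroconversion. Assume a symptom-prompted sample comes from someone who meets the COVID-19 symptom criteria, and a scheduled or exposure-prompted sample from someone without symptoms.

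| Specimen | Trigger | Component endpoint met | Text of 6.5.1.1 | Table 1 cell alone |
|---|---|---|---|---|
| NP | Scheduled | Asymptomatic | Yes | Yes |
| NP | Symptoms | COVID-19 | Yes | Yes |
| NP | Exposure | Asymptomatic | Yes | No |
| Nasal | Symptoms | COVID-19 | Yes | No |
| Nasal | Exposure | Asymptomatic | Yes | No |
| Saliva | Symptoms | COVID-19 | Yes | No |
| Saliva | Exposure | Asymptomatic | Yes | No |
| Hospital, non-NP | Symptoms | COVID-19 | Yes | No |

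The text counts 8 of 8. The cell alone counts 2 and omits 8 − 2 = 6. These are kinds of case, not numbers of participants.

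**Step 2: scheduled swabs inside the counting windows.** Windows are from SAP 6.5.2 and swab days from Protocol Tables 7 to 10. Length is last day − first day + 1.

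| Group | Window | Length (days) | Scheduled NP swabs in window |
|---|---|---|---|
| A1, A5 | Day 43 to 394 | 394 − 43 + 1 = 352 | Day 57 |
| A2 | Day 99 to 450 | 450 − 99 + 1 = 352 | Day 113 |
| A3 | Day 15 to 365 | 365 − 15 + 1 = 351 | Day 29 |
| Part B | BD-Day 15 to 181 | 181 − 15 + 1 = 167 | None (BD-Day 1 is pre-dose) |

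Under the cell alone, a symptom-free infection can be found by RT-PCR on one scheduled day per Part A group and on none in Part B.

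**Step 3: what could recover an omitted case.** The serology row applies whatever the RT-PCR specimen was. Post-dose samples that can show conversion are taken at widely spaced visits: Days 57, 209 and 394 in A1 and A5, and BD-Days 29 and 181 in Part B. A participant who does not seroconvert, or is not sampled, stays out. One who does may be dated later if the RT-PCR result is disregarded.

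**Step 4: which statement governs.** No sentence in the SAP ranks table against text. The protocol cannot settle it, because SAP Section 1 says the SAP prevails where the two differ. SAP Section 7 lists no change from the protocol, so nothing marks the narrower cell as deliberate.

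**The case against.** The strongest reply is that the SAP, read as a whole, already counts these cases. The opening sentence of 6.5.1.1 makes the endpoint the union of its components. The RT-PCR criterion in the text is unrestricted, as is the dating rule below the table. Table 1 is described as a summary. An analysis of infection by nasal and saliva specimen (6.5.2) would make little sense if those specimens were excluded. NP swab may simply be shorthand: 6.5.1.3 also describes the illness visit as collecting an NP swab, although its case definition accepts other samples. All of this stands, and it shows what was probably intended.

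It also rules out three stronger readings that a reader might infer:

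- **That these participants are not infections under the plan, so rates are biased down.** This follows only if the cell is applied alone and overrides the text.
- **That positives on BD-Day 2 to 14 would count early**, because the cell names only the second and third dose. The counting line below Table 1 requires 14 days from the booster, and 6.5.2 starts the booster windows at BD-Day 1 + 14.
- **That local laboratory results are excluded.** The cell says nothing about the laboratory, so it does not conflict with SAP 3.2.2. A hospital NP swab prompted by symptoms also fits the cell; only other hospital samples fall outside it.

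The stakes are modest as well. Overall infection is not listed separately among the SAP Section 3 endpoints, the COVID-19 and asymptomatic endpoints do not use Table 1, and no hypothesis is tested. None of this removes the conflict between a stated derivation rule and the definition it is meant to implement.

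**Conclusion.** The RT-PCR cell of Table 1 is wrong as written: it contradicts the text of its own section on specimen, on trigger and on the booster. The consequence is conditional. If the endpoint is programmed from the table, six of the eight kinds of RT-PCR-confirmed case are omitted unless serology recovers them, no symptom-free RT-PCR positive counts in Part B, and the infection summary fails to reconcile with its components. If it is programmed from the text, nothing is lost.

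The number of participants affected cannot be computed, because the documents give no frequency of testing by specimen or trigger. The comparison rests on the symptom assumption in Step 1. It also does not treat the convalescent NP swab, taken about 28 days after diagnosis, as a scheduled swab. If it were so treated, a symptomatic participant still positive then could be recovered. The Part B statement about symptom-free positives would not change, since Protocol 7.1.6 ties that visit to symptomatic infection.

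**What to change.** Replace the RT-PCR cell of Table 1 with: *RT-PCR positive on any specimen that Section 3.2.2 accepts, from a scheduled, illness or other unscheduled visit (exposure-prompted visits included), 14 days or more after the second dose, third dose or booster.* Add one sentence below the table stating that every case under 6.5.1.2 or 6.5.1.3 is also a case under 6.5.1.1, which gives the programmers a direct check.

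The cost is one cell and one sentence. No new data, visits or sample size are needed, and the change agrees with the existing text of 6.5.1.1. If outputs have already been programmed from the table, the infection summaries need to be rerun.
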